2.8.3. Data Analysis

The CAPS and PDS scores will be analyzed by nonparametric methods for analysis of variance (cf. Brunner and Langer (2002), Brunner, Domhof and Langer (2002)). The nonparametric framework is chosen for two reasons, that of the sample size being too small to assess the assumptions that underlie a parametric model, and because the primary outcome measure, CAPS score, is only measured on an ordinal scale. We will also compute descriptive statistics for Stage 1 and Stage 2 CAPS and PDS scores for all participants enrolled in Stage 2. It is unlikely that there will be enough participants in Stage 2 for formal analysis, but scores can be compared across the two stages to see whether Stage 2 scores are reduced compared with Stage 1 scores. Finally, we will compute CAPS and PDS scores for any participant undergoing “Stage 3”.

The first step of the analysis will consist of descriptively summarizing the data by graphing the time course of CAPS for each patient and by computing summary measures for CAPS. The second step will consist of testing the above-mentioned hypothesis. In order to compare the time courses of the control group and the treatment group, we will apply a so-called F1_LD_F1 (cf. Brunner and Langer (2002), Brunner et al. (2002)) with experimental intervention condition (MDMA versus active placebo) serving as a between-group factor and time of measurement serving as a within-subjects factor. We are mainly interested in testing an interaction between experimental intervention condition and time. We expect all participants will have lower CAPS scores two months after the third experimental session than at baseline, but that people given the fully active dose will have lower CAPS scores than people given active placebo. The hypothesis concerning only the treatment group will be analyzed by

comparing differences between subject's baseline CAPS and treatment scores at various time points. This can be done with Wilcoxon's Signed-Rank-Test for paired data. We expect that people will have lower CAPS scores after the third experimental session than after the second experimental session.

Statistical significance will be set at 0.05. Because the sample size is very small, the study has sufficient power only to detect large effects. Therefore, there will be no adjustment for multiple testing; p-values and confidence intervals will be reported instead. We will assess participant CAPS and PDS scores at baseline and two months after each participant has undergone a final session, defined as the last experimental or open-label MDMA-assisted psychotherapy session, using the same nonparametric tests employed in comparisons of active placebo and experimental dose MDMA described above.

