2.8. Methods

2.8.1. Drugs and Dosage

Upon enrollment in the study, the participant will be randomly assigned to the Low Dose or the Fully Active Dose condition. Condition assignment will be performed with a table of random numbers generated by the Institute for Statistics, University of Bern. All study investigators will remain blind to condition assignment. If there is an adverse event or other emergency requiring knowledge of participant's condition assignment, the blind may be broken for an individual participant.

Participants in the Low Dose condition are assigned to receive an initial dose of 25 mg MDMA followed 2.5 hours later by a supplemental dose of 12.5 mg MDMA. Participants assigned to the Fully Active dose condition will receive an initial dose of 125 mg followed 2.5 hours later by a supplemental dose of 62.5 mg MDMA. Eight of 12 subjects, or 66.6%, will be assigned to the Fully Active dose condition, and 4 of 12, or 33.3%, will be assigned to the Low Dose condition.

The two doses of MDMA chosen for the Low Dose condition have been selected on the basis of their ability to produce minimal but detectable subjective effects (Grob et al. unpublished; Harris et al. 2002) and thus serve as an active placebo. The cumulative dose of 37.5 mg MDMA is not expected to produce a significant reduction in anxiety or a significant increase in access to emotionally upsetting material, though this dose may produce slight alterations in consciousness, such as increased relaxation or tension (Harris et al. 2002). The initial 125 mg dose of MDMA selected for the Fully Active Dose condition was chosen on the basis of case reports of MDMA-assisted psychotherapy conducted in the US prior to scheduling (Greer and Tolbert 1986), as well as on data obtained from [name] MAPS-sponsored MDMA/PTSD pilot study currently underway in the United States. This dose is expected to reduce fear in response to emotionally upsetting thoughts, feelings or memories and to increase access to emotionally intense material, and is thus expected to be therapeutically active. Doses equal to or exceeding 125 mg have been employed in previous uncontrolled and controlled studies of MDMA (Cami et al. 2000; Grob et al. 1996; Grob et al. Unpublished; Harris et al. 2002; Lester et al. 2000; Mas et al. 1999; Styk 2007; Tancer et al. 2001; Tancer et al. 2003; Vollenweider et al. 1998).

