3.1 Primary Objective

To evaluate changes in PTSD symptoms via CAPS scores gathered at baseline, three weeks after the second experimental session, and three weeks after the third experimental session.

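### Protocol 2.8.3 leaves the statistic, visits and reference distribution of its main CAPS test open: at 8 v 4 on T0–T2 its usual large-sample form runs at about 7–8% (ANOVA-type) or 15–16% (Wald-type), not 5%, and the SAP names a different test

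*Protocol*

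**What the plan says.** Protocol 2.8.3 adopts rank methods for CAPS and PDS because CAPS is ordinal and because of "the sample size being too small to assess the assumptions that underlie a parametric model". For the between-arm test it states: "In order to compare the time courses of the control group and the treatment group, we will apply a so-called F1_LD_F1". Condition is the between-group factor and time the within-subject factor. Its focus is explicit: "We are mainly interested in testing an interaction between experimental intervention condition and time". The level is equally explicit: "Statistical significance will be set at 0.05". There is no multiplicity adjustment, and the section accepts that only large effects are detectable. Section 2.8.1 sets the split: "Eight of 12 subjects, or 66.6%, will be assigned to the Fully Active dose condition". That leaves 4 on the low dose.

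Three things are not stated:

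- **Statistic.** F1_LD_F1 has an ANOVA-type and a Wald-type form. Neither is named.
- **Visits.** Section 2.8.2 lists six assessments, T0 to T5. The only endpoint named beside the test is T3: "We expect all participants will have lower CAPS scores two months after the third experimental session than at baseline".
- **Reference distribution.** No exact, permutation or small-sample reference is mentioned.

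The SAP goes another way. Its primary objective (3.1) uses "CAPS scores gathered at baseline, three weeks after the second experimental session, and three weeks after the third experimental session", that is T0, T1 and T2. Its main analysis (6.4.1) is a repeated-measures ANOVA on those visits. It does not mention the rank method.

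**The concern.** Ranking removes the normality assumption. It does not remove the large-sample approximation that usually supplies the interaction p-value. That approximation relies on rank covariances estimated separately in each arm, and one arm has 4 people. The stated reason for the method, a very small sample, is therefore also a reason to doubt its usual p-value.

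At stake is the meaning of a significant result on the primary outcome. The protocol warns of low power but not of an error rate above 5%, so a reader would take a p-value just under 0.05 at face value. Because the statistic is unnamed, the same data could be tested at two quite different true levels, and nothing in the text prevents that choice being made after the results are known.

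**Working it through.** **The plan's own figure.** The only figure is the level, 0.05. No power or sample-size calculation is given. The question is whether the named test delivers that level at 8 v 4.

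**Inputs from the documents**

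- N = 12, split 8 v 4 (protocol 2.8.1).
- Condition-by-time interaction, level 0.05 (protocol 2.8.3).
- Base case of three visits, T0–T2. These are the SAP's primary visits (3.1). They are also the blinded randomised window, because each participant is unblinded at T2 and low-dose participants are then offered Stage 2 (protocol 2.8.6).

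**Assumptions (the documents give no SD or correlation).** Both arms share one distribution (the null). Within-person correlation runs from 0 to 0.9, equal or AR(1). Scores are normal, skewed, rounded or of unequal variance over time. The common time trend is 0 to 1.5 SD.

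**Statistics.** Mid-ranks are taken over all N × t scores. Let p be the vector of estimated relative effects, V the block-diagonal covariance estimate (one block per arm), C the interaction contrast and T = C'(CC')⁻C.

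- ANOVA-type: A = N·p'Tp / tr(TV), referred to F(f, ∞) with f = tr(TV)² / tr(TVTV).
- Wald-type: W = N·p'C'(CVC')⁻Cp, referred to chi-square with t − 1 degrees of freedom.

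**True level at nominal 5%, 8 v 4** (40,000 to 100,000 null trials for most settings, Monte Carlo s.e. about 0.1 point)

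| Visits | ANOVA-type | Wald-type |
|---|---|---|
| 2 | 9.1–9.3% | 9.1–9.3% |
| 3 (T0–T2) | 7.1–7.8% | 15.1–16.0% |
| 4 (adding T3) | 5.9–7.1% | 24–25% |
| 5 | 4.7–6.4% | 34–36% |
| 6 | 3.9–6.1% | 47–49% |

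A separate simulation with integer CAPS scores, SD 12 at baseline and 25 later, and correlations 0.4–0.8 gave 7.0–8.1% and 15–16% for three visits. At three visits the result barely moves with the assumed SDs and correlations.

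**Is the small sample the cause?** Three visits, larger arms:

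| Arms | ANOVA-type | Wald-type |
|---|---|---|
| 16 v 8 | 6.5% | 10.1% |
| 40 v 20 | 5.5% | 6.7% |
| 200 v 100 | 5.4% | 5.6% |

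The levels fall towards 5% as the arms grow. No packaged implementation of the method was available for a cross-check.

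**Nominal p-value that corresponds to a true 5%.** ANOVA-type: about 0.027–0.030 with three visits and 0.038–0.041 with four. Wald-type with three visits: about 0.003.

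**Permutation reference.** The number of 8:4 splits is C(12,4) = (12·11·10·9)/(4·3·2·1) = 11,880/24 = 495. The smallest attainable p is 1/495 = 0.002. Since 0.05 × 495 = 24.75, the largest attainable level not above 5% is 24/495 = 4.85%. Simulated levels over 10,000 trials (s.e. about 0.2 point) were 5.0% (ANOVA-type) and 5.1% (Wald-type) with three visits, and 5.2% and 4.7% with four. All agree with 4.85% within simulation error.

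**Power.** Under the SD 12/25 assumptions (5,000 trials, s.e. about 0.7 point), permutation v large-sample power was 37.0% v 38.5% at a 25-point shift and 67.0% v 67.6% at 37.5 points. The differences are 1.5 and 0.6 points.

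**The SAP's test.** Repeated-measures ANOVA at 8 v 4 held 4.9% with three or four visits under normality and equal correlations. With AR(1) correlation 0.7 and no sphericity correction it gave 5.6% (three visits) and 6.4% (four).

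**The case against.** The strongest reply is that the inflation depends on choices the protocol never makes. Section 2.8.3 names neither visits nor statistic. The nearest endpoint in the text is T3, and T0–T2 is borrowed from the SAP, where the test is different. With four visits the ANOVA-type excess is only about 1 to 2 points, and with six it is about zero or negative. Nor does the protocol say that a large-sample reference will be used; that is inferred from how the method is usually run. This objection stands, and it is why every figure here is tied to a stated schedule and statistic. It does not remove the gap: the text specifies nothing that would hold the level.

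A second reply is that the SAP replaces the test and that its ANOVA holds about 5% in the simplest case. This also stands. A reader might infer that the trial's efficacy result as analysed carries a 7–16% error rate. The documents do not support that if the SAP governs. What remains is two main tests for one outcome. The SAP's choice also drops the protocol's reason for avoiding parametric models without explanation.

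Two further inferences should be resisted. This is not the only controlled efficacy comparison: PDS, CAPS subscales and diagnostic status are also compared between arms (protocol 2.8.3; SAP 6.4.1 and 6.4.2). Nor does phase III hang on this p-value: the protocol's introductory statement ties that decision to the sponsor's pilot studies together, and section 2.6 hypothesises only trends. Both points lower the severity.

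**Conclusion.** The concern holds in conditional form. If F1_LD_F1 is run on T0–T2 with its usual large-sample reference at 8 v 4, the ANOVA-type form exceeds the stated level by about 2 to 3 points and the Wald-type form runs at about three times it. The Wald-type form worsens with each added visit; the ANOVA-type form improves.

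It is tempting to say outright that the protocol's 0.05 is really 7–8% or 15–16%. The documents do not support that, because they fix neither the visits, the statistic nor the reference. The established defect is under-specification of the protocol's main test, with a real inflation under its most natural reading, together with a conflict with the SAP over which test is the main one. The conclusion rests on assumed score distributions and on exactly 12 analysed participants. It is a should-fix point.

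**What to change.** - **Name one test.** State the same between-arm CAPS test on T0, T1 and T2 in protocol 2.8.3 and SAP 6.4.1, and name the rank-based condition-by-time statistic.
- **Take its p-value by re-randomisation.** Recompute the statistic over every allocation that the actual scheme allows and report the share at least as extreme as observed. That set has 495 members only if exactly 12 are analysed in an unrestricted 8:4 split. Protocol 2.8.1 does not state any blocking, 2.7 replaces drop-outs, and the intention-to-treat set in SAP 6.1 keeps anyone randomised who had one session. The set must match all three.
- **Report an estimate.** Give the arm difference in change from T0 to T2 with a 95% confidence interval from inverting a randomisation test of that difference over the same allocations. State that this assumes a constant shift. It also supplies the intervals that 2.8.3 promises.
- **Secondary display.** If F1_LD_F1 output is kept, show the ANOVA-type statistic only and call its level approximate.
- **Date the change.** SAP 8.0 records that outcome data had already been presented in 2010 and 2011, so the amendment should say when the test was chosen relative to those data.

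**Cost.** Wording in two documents, a short script outside SPSS (the package named in SAP 6.1), and little or no change in power: within about 1–3 points either way in the scenarios simulated.

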1.0 Definitions

Categorical data: This refers to discrete (indivisible) variables, such as gender or ethnicity. These data will be presented as total numbers of each category as needed to describe the sample.

Descriptive data: This includes mean, median, standard deviation, minimum and maximum of numerical data used as needed to describe the sample.

Difference scores: These consist of scores computed by subtracting one value from another, as subtracting baseline from End of Stage 1 score, used to test for differences between and within groups to determine change as a function of experimental treatment over time.

Efficacy: A type of analysis used to assess therapeutic effects or benefits.

Exploratory analyses: An inferential or descriptive analysis of the data to determine trends that might lead to hypotheses for further study.

Frequency listing: A tabular listing of numbers and/or percentages of events used as needed to describe the sample or data characteristics.

Outcome measures: These are primary and secondary study measures that are used to test the study hypotheses.

Process measures: These are study measures or qualitative observations collected during the study that may increase depth of understanding and that are not necessarily related to safety or efficacy.

Protocol deviation: An event that represents significant divergence from the intended study design as described in the protocol.

Safety: An assessment of the condition of study subjects that examines potential risks, adverse events and reactions.

Safety measures: These are study measures that assess safety, such as blood pressure monitoring. These measures are used to assess safety of the study drug.

Study design: All elements of a research project that define the study question, experimental methods, study procedures including blinding and randomization, measurement techniques, flow sheet of data, and statistical analysis.

Tabular Listing: A list of each variable or item for each individual subject either in total or by condition in a table format.

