6.4.1 Main analyses

Goal: To determine if there is a main effect of condition on PTSD symptoms and criteria for meeting PTSD, three weeks after the second experimental session and three weeks after the third experimental session 1.

Population: Intention to Treat and Per protocol

Data included in analyses: CAPS (Global Score, subscales, and Diagnostic criteria met)

Format of analyses: Repeated-measures ANOVA. If multiple scores from a single scale are assessed, Bonferroni corrections were applied.

Time: Baseline, 3 weeks after Exp. Session 2, 3 weeks after Exp. Session 3

Between-groups factors: Condition (125 mg MDMA, 25 mg MDMA)

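### No Stage 1 between-arm efficacy analysis adjusts for baseline CAPS; the power this costs depends on assumptions the documents do not supply, and a permutation or rank-based ANCOVA should be added

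*Protocol*

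**What the plan says.** Protocol 2.8.3 compares the arms with the rank-based F1_LD_F1 layout, with "time of measurement serving as a within-subjects factor", and adds: "We are mainly interested in testing an interaction between experimental intervention condition and time". For the treatment group alone it compares baseline with later scores: "This can be done with Wilcoxon's Signed-Rank-Test for paired data". That is a within-arm test, and ANCOVA is not its alternative.

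SAP 6.4.1 gives "Format of analyses: Repeated-measures ANOVA". Its time levels are baseline, three weeks after session 2 (T1) and three weeks after session 3 (T2), and its stated goal is a main effect of condition. SAP 1.0 describes difference scores as "subtracting baseline from End of Stage 1 score, used to test for differences between and within groups".

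The demographic analyses in SAP 6.4.2 use age, gender, years of psychotherapy and other affective disorder as predictors, but not baseline CAPS.

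On size and error rate, Protocol 2.8.1 says "Eight of 12 subjects, or 66.6%, will be assigned to the Fully Active dose condition". Protocol 2.8.3 says "Statistical significance will be set at 0.05" and "Because the sample size is very small, the study has sufficient power only to detect large effects".

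**The concern.** Baseline CAPS (T0) is measured before dosing in every participant and probably predicts later CAPS. There are three ways to use it in a between-arm comparison:

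- as a repeated level, as in the protocol interaction and the SAP ANOVA;
- by subtracting it with a coefficient fixed at 1, as in a change score;
- as a covariate whose coefficient the data estimate.

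The plan uses the first, defines the second and omits the third. The interaction test spreads a T2 effect over 2 degrees of freedom. With equal SDs, full subtraction carries more baseline noise than needed. A main effect averaged over all three levels includes one at which no treatment effect can exist. In a trial that concedes it can detect only large effects, with four controls, power lost through the handling of baseline matters.

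**Working it through.** The plan states no power, SD, effect size or CAPS correlation, so there is no figure to reproduce. The only correlation in the documents is the PDS retest value of 0.74 (Protocol 2.8.2), which is for another scale over a short interval.

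**From the documents:** alpha 0.05 (two-sided assumed for the t-tests); 8 v 4, so 1/8 + 1/4 = 0.375.

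**Assumed:** normal data, SD 1 at each time, the same correlation ρ between any two times, an effect of 1.5 SD at T2, and either half (0.75) or all (1.5) of it at T1.

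**Formulas**

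1. *ANCOVA of T2 on T0.* Variance of the adjusted difference = (1 − ρ²)(0.375 + D²/S), where D is the chance difference in baseline means and S the within-arm baseline sum of squares. 9 df, averaged over simulated baselines (mean variance inflation 1.12).
2. *Change score T2 − T0.* Variance = 2(1 − ρ) × 0.375; 10 df. At ρ = 0.5 the noncentrality is 1.5/√0.375 = 2.45.
3. *Interaction F (2, 20 df).* Noncentrality = sum of squared deviations of the three arm differences from their mean, divided by 0.375(1 − ρ).
   - Half effect at T1: differences 0, 0.75, 1.5; sum 1.125; noncentrality 3/(1 − ρ).
   - Full effect at T1: differences 0, 1.5, 1.5; sum 1.5; noncentrality 4/(1 − ρ).
4. *Main effect of condition.* Arm difference averaged over three times = 0.75 (half) or 1.0 (full); variance = (1 + 2ρ)/3 × 0.375; 10 df.

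**Power (%)**

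| Test | ρ = 0.3 | ρ = 0.5 | ρ = 0.7 |
|---|---|---|---|
| ANCOVA | 58.7 | 66.8 | 82.3 |
| Change score | 46.5 | 59.9 | 81.3 |
| Interaction, half at T1 | 38.7 | 51.7 | 74.9 |
| Interaction, full at T1 | 49.6 | 64.7 | 86.6 |
| Main effect, half at T1 | 32.9 | 27.4 | 23.6 |
| Main effect, full at T1 | 52.4 | 44.0 | 37.9 |

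**ANCOVA minus the alternative (points)**

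| Against | ρ = 0.3 | ρ = 0.5 | ρ = 0.7 |
|---|---|---|---|
| Change score | +12.2 | +6.9 | +1.0 |
| Interaction, half at T1 | +20.0 | +15.1 | +7.4 |
| Interaction, full at T1 | +9.1 | +2.1 | −4.3 |
| Main effect, half at T1 | +25.8 | +39.4 | +58.7 |
| Main effect, full at T1 | +6.3 | +22.8 | +44.4 |

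Direct simulation agrees within about one point, with ANCOVA type I error near 5%. At ρ = 0.8 ANCOVA is about 1 point below the change score (92.6 v 93.6).

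**Rank statistic.** The protocol's test is rank-based, so the interaction rows are only a guide. In simulation over ρ 0.3 to 0.8 and effects of 0.8 to 2.0 SD, ANCOVA's gain over the rank interaction was −2.0 to +6.4 points with the full effect at T1, and +2.2 to +17.7 with two thirds of it there. The rank test's own type I error was about 7 to 8%, which flatters its power.

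**Entry floor.** Selection on T0 (CAPS of 50 or higher) lowers the correlation but leaves the regression slope and residual variance unchanged. The change score's penalty is (1 − slope)² × Var(T0), which shrinks as the baseline range narrows. With baseline truncated 1 SD below its mean, ANCOVA's gain over the change score is about +7, +2 and −1 points (untruncated ρ 0.3, 0.5, 0.7). Truncated at the mean, it is about +2, −1 and −3.

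**The case against.** The strongest reply is that any single power figure comes from the assumptions. That stands. If the response is complete after two sessions and the correlation is 0.7, the planned interaction test beats ANCOVA. Hypothesis 3 in Protocol 2.6 expects further gain from the third session, which favours a graded profile but does not fix one. Full subtraction is also not always wasteful: it is optimal when ρ × SD(T2)/SD(T0) equals 1, which can occur if the entry floor makes baseline less variable than outcome.

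Three other points stand in part:

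- SAP 1.0 is a glossary. No main analysis is a between-arm t-test on change, so that comparison is secondary.
- The interaction and the change score already measure change from baseline. Handling chance imbalance is therefore not a distinctive benefit of ANCOVA against them, only against the main effect.
- Protocol 2.8.3 avoids parametric models because n is too small to check assumptions and CAPS is treated as ordinal. A purely parametric ANCOVA would contradict that reasoning.

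Choosing T2 does narrow a time-course question to one visit, and Protocol 2.8.3 phrases its expectation at two months after session 3. But SAP 3.1 ends the primary objective at T2, and Protocol 2.8.6 breaks each participant's blind after T2 and offers low-dose participants open-label treatment. T2 is therefore the last visit before unblinding.

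A reader might infer that this trial loses some 7 to 20 points however baseline is handled. The documents do not support that: the range belongs to one test under one assumed profile. A reader might also infer that the entry floor strengthens the case; against a change score it weakens it.

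**Conclusion.** The omission is plain in both documents. Its cost is real in many plausible settings but cannot be fixed from the text. The gain over the parametric interaction can be substantial or negative, and the gain over a change score is modest and vanishes at high correlation.

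The largest and most consistent shortfall is in the main effect named as the goal of SAP 6.4.1, which loses power in every setting examined. That also leaves the protocol's interaction and the SAP's main effect to be reconciled.

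All of this rests on normality, equal SDs, equal correlations and a 1.5 SD effect. None of it shows the planned tests to be invalid. It supports adding a baseline-adjusted analysis.

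**What to change.** In SAP 6.4.1, add a Stage 1 comparison of CAPS Global Score at T2 on condition with T0 CAPS as covariate. Take the p-value from a permutation test that follows the actual allocation scheme, or use a rank-based ANCOVA. Report the estimate with a confidence interval. Keep the repeated-measures or F1_LD_F1 test beside it, and state which effect, interaction or main, that test targets.

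SAP 4.0 is written largely in the past tense, and SAP 8.0 says preliminary outcome data were presented in 2010 and 2011. If the addition follows those presentations, say so, so that it is not read as prespecified.

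The cost is a short insertion using data already collected, one error degree of freedom (9 instead of 10) and a common-slope assumption that 12 participants cannot check well. The permutation p-value protects the error rate, but does not make the slope assumption true.
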